## **5.0 SCHEDULED ASSESSMENTS**

### **5.1 Screening (Visit 1) and Baseline (Visit 2) Assessments**

The screening assessment (Visit 1) will occur within 3 months of the first training session. The baseline assessment (Visit 2) will occur within one week of the first training following commencement of the study. These assessments will include the following tests or procedures:

1. Documentation of demographic information, including gender, age, allergies, and current medications (screening visit 1).
2. Clinical examination of the ears (screening and baseline visit 1 and 2).
3. Documentation of key clinical data such as confirmation of thresholds being  $\leq 25$  dB HL up to 4 kHz,  $\leq 30$  dB HL at 4 kHz, and  $\leq 45$  dB HL at 6 and 8 kHz, and the absence of any ear disorder (screening visit 1).
4. Blood draw for laboratory testing that include a serum pregnancy test\*, electrolyte panel, BUN, Cr, ALT, and AST and DNA analysis will be collected (baseline visit 2).

\*Women capable of becoming pregnant will be asked to have a pregnancy test before beginning this study. Women capable of becoming pregnant will be instructed to use effective birth control methods and not to become pregnant while participating in this study as there may be unknown risks to the unborn child. There may be long-term effects of the treatment being studied that could increase the risk of harm to an unborn child. The study team must be notified if the birth control method fails while on the study and/or if the participant becomes pregnant while participating in this research study.

5. Audiogram, ECochG, DPOAE, and WIN testing to document baseline measurements (baseline visit 2).

**Audiometry:** The audiogram will be performed to look for TTS and PTS. Earphones will be placed over the participant's ears and a series of tones at a soft volume will be played at varying frequencies. The participant indicates that they hear the tones by pressing a button. Thresholds will be measured from .025-16 kHz. If there is an absence of a threshold at the limits of the equipment, the threshold will be reported as equipment limits (in dB HL) + 10 dB HL. As with the DPOAE, all equipment and procedures are based on a clinically approved protocol. Each ear will be tested separately.

**Electrocochleography (ECochG):** An ECochG is an electrophysiological measurement of the cochlea in response to sound. It is a clinically-approved auditory evoked potential that is used to evaluate the status of both the cochlea and the auditory nerve fiber. This measurement is obtained by inserting a soft gold-foiled earphone into the participant's ear. This earphone serves to deliver a series of clicks, as well as an electrode to measure the electrophysiological response of the cochlea to the sound. The electrode montage is completed with a ground electrode on the forehead at midline and a gold-foil electrode in the contralateral ear to serve as the inverting electrode. The impedance between electrodes will be  $< 3 \text{ k}\Omega$  for all participants. The click stimuli at 90 dB nHL used for the study will be repeated 2000 times so that the recording signal can be averaged with artifact rejection. The measurement will be repeated three times. Testing time will take 45 minutes to 1 hour.

**Distortion Product Otoacoustic Emissions (DPOAE):** DPOAEs are a measure of outer hair cell function and will be used as an indicator of changes in cochlear health and possible PTS in the early period following noise exposure. A soft earphone will be inserted into the participant's ear and a series of tones at a comfortable volume will be played at varying frequencies. No participation is required of the participant as DPOAE are an objective assessment of cochlear health. The measurement system (Interacoustics Titan DPOAE440) will record the level of the emissions evoked by two primary tones, f1 and f2 ( $f_2/f_1 = 1.22$ ) at levels 65 and 55 dB SPL respectively. The f2 primary tone will be swept from 1- 6 kHz, and will be repeated at least five times per session in order to calculate the stability of the emission at each session. All data will be identified and stored on a password protected computer. DPOAE recording will take about 20 minutes to complete.

**Words in Noise Test (WIN):** Earphones will be placed over the participant's ears and the WIN test will presented to each ear separately. The WIN test battery consists of 35 words that are presented in a background noise (speech babble) with varying degrees of signal-to-noise ratios (SNR) from 24 dB HL to 0 dB HL. The babble is set at 80 dB SPL, and the target word levels decrease from 104 dB SPL to 80 dB SPL. The SNR at 24 dB HL is the easiest, with words presented at 24 dB above the noise background, whereas the SNR of 0 dB is the most difficult with target words being presented at the same level as the background noise (Wilson and Burks, 2005; Wilson and Watts, 2012). The WIN will be repeated three times in order to assess test-retest reliability. The total number of words correctly identified will be used to calculate a dB HL S/N threshold by the Spearman-Karber equation at the mean of 50% correct points. All of speech testing will take 10-15 minutes to complete.

6. Baseline sound measurements will be obtained at the start of each test session, including the peak ambient noise level and the average noise level (screening and baseline visit 1 and 2).
7. Completion of participant questionnaires, including (screening visit 1):
  - a. Case history form
  - b. Life Exposure to Noise and Solvents (LENS-Q) (Full)
  - c. Life Exposure to Noise and Solvents (LENS-Q) (Adapted)
  - d. Tinnitus Functional Index (TFI)
8. Completion of baseline cognitive assessments, including (baseline visit 2):
  - a. Digit-symbol substitution test: Measures processing speed
  - b. List learning task/RBANS: Measures memory function.
  - c. Verbal fluency test (word finding task): Measures working memory, speech/language.
  - d. Stroop test: Measures executive functioning (vigilance, attention, inhibition).

All data will be identified and stored on a password protected computer.

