### **3.1b Enrollment Inclusion Criteria**

1. Observed audiometric TTS  $\geq$  10 dB HL at 2, 3, 4 and/or 6 kHz

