### **3.2 Exclusion Criteria**

1. History of known sulfa allergy or hypersensitivity to carbonic anhydrase inhibitors.
2. History of moderate-to-severe kidney or liver disease.
3. Acute viral, bacterial, fungal or parasitic infection.
4. History of seizures.
5. Currently pregnant or breast-feeding.
6. Any current or history of otologic disorder.
7. History of ototoxic drug use.
8. Current use of strong/moderate 3A4 inhibitor/inducer and grapefruit juice.

Note: For secondary outcomes analysis only, exclusion criteria is as follows:

- a) DPOAE data will be used as a secondary outcome measure of TTS, and participants will be excluded if their DPOAE is absent at more than 4/10 frequencies. Criteria for a present response is any response that is  $> 5$  dB SPL above the noise floor and replicable within  $\pm 5$  dB SPL.
- b) ECochG: Participants will be excluded if the ECochG/ABR wave I response is absent.
- c) WIN test: Participants with WIN scores greater than moderate difficulty or 14.9 dB SNR will be excluded.

Participants will not be excluded from the study for not meeting secondary outcome criteria.

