## 9.0 STUDY CALENDAR

	VISIT 1 Screening Assessment	VISIT 2 Baseline Assessment	Post-training		
			VISIT 3 Within 5-30 Minutes	VISIT 4 Within 24 Hours	VISIT 5 30 days (+/- 3 days)***
Informed Consent	X				
Demographic Info	X				
Current Meds	X				
Questionnaires	X				X
Cognitive Assessment		X		X	
Clinical ear exam	X	X	X		X
Audiogram	X	X	X		X
ECochG		X			X
DPOAE		X	X		X
WIN		X			X
Sound Measurements	X	X	X		
Randomization			X*		
Oral Dose* ZNS or Placebo			X**		
Blood draw**		X		X	
AE Assessment			X	X	X

\* Dispensed after training if TTS is identified on audiogram 5-30 minutes after shooting.

\*\* Blood draw: Electrolyte panel, BUN, Cr, ALT, and AST; DNA analysis and serum pregnancy test at baseline

\*\*\* If TTS is seen from pure tones after each training session

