## 10.0 DATA SUBMISSION SCHEDULE

Case report forms with appropriate source documentation will be completed according to the schedule listed in this section.

Case Report Form	Submission Schedule
Original Consent Form	Prior to study activities
Eligibility Form	At time of consent; Prior to firearm training
Firearm Training Form	Time of firearm training
Adverse Event Form	Continuous

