6.4 Concomitant Medications

Concomitant medications are defined as all medications (excluding study dose) taken on or after the date of first dose administration up to and including the date of the post training Day 30 visit (Visit 5).

Medications that started before the date of first dose and are ongoing after the date of first dose will be considered as concomitant medications.

Medications will be coded using the Anatomical Therapeutic Chemical (ATC) classification codes and preferred drug name according to the World Health Organization (WHO) Drug Global B3, (March 2021). Summary table will be provided for concomitant medications for the Safety Sample Set, presenting the number and relative frequency of subjects by treatment group, and will be sorted in alphabetical order of ATC Level 2 and then PT in the overall column. For each participant, the medication will be counted only once within a given ATC level 2 and only once within a given preferred drug name level. A participant may appear more than once if she has more than one concomitant medication coded under different ATC categories.

Concomitant medications will be presented in a listing.

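### Medications are scheduled to be recorded only at Visit 1, so exclusion 8 has no scheduled medication check near dosing and the SAP's concomitant-medication table cannot be produced as defined

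*Protocol*

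**What the plan says.** **Recording.** Protocol 5.1, item 1, assigns the medication record to Visit 1: "Documentation of demographic information, including gender, age, allergies, and current medications (screening visit 1". The medication row of the calendar in Protocol 9.0 and of its copy in SAP 2.6 has one mark, under Visit 1. The written medication list is part of the Case History Form (Protocol Appendix D), which 5.1 item 7 also places at Visit 1. Its columns are drug, strength, frequency, route and reason.

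**Timing.** "The screening assessment (Visit 1) will occur within 3 months of the first training session". The study drug comes later, at Visit 3: "Dispensed after training if TTS is identified on audiogram 5-30 minutes after shooting".

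**Eligibility.** Exclusion 8 in Protocol 3.2 reads "Current use of strong/moderate 3A4 inhibitor/inducer and grapefruit juice". Exclusion 3 reads "Acute viral, bacterial, fungal or parasitic infection". Neither names a visit. The one criterion in Protocol 3.1b, applied after shooting, is "Observed audiometric TTS" of a stated size. Protocol 5.2 and SAP 2.4 nevertheless confine randomisation to eligible participants. Protocol 10.0 gives the Eligibility Form's schedule as "At time of consent; Prior to firearm training".

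**Reporting.** SAP 6.4 defines concomitant medications as those "taken on or after the date of first dose administration up to and including the date of the post training Day 30 visit", and adds drugs begun earlier that continue past the dose. They are to be coded, tabulated (Table 14.1.5) and listed (Listing 16.1.6) for the safety sample.

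**The concern.** The plan asks two things of its medication data that a single early record cannot supply.

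First, exclusion 8 concerns a state that can change within weeks. A record up to 3 months old says little about what an officer is taking when the kit is assigned. Because no visit is named, a site could reasonably judge the criterion at screening, before training or on the shooting day, and the schedule supplies medication data only for the first of these.

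Second, SAP 6.4 describes a period that begins on the dosing day, after the only scheduled record. A drug started between Visit 1 and Visit 5 has no scheduled place to be written down. That includes an ototoxic drug begun before the Day 30 audiogram, which supplies the primary endpoint.

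At stake are the completeness of the safety reporting and the soundness of the per-protocol sample. SAP 7 runs every efficacy analysis on that sample as well as on the intention-to-treat sample. SAP 4.4 limits it to subjects treated in compliance with the protocol, and SAP 6.6 names unmet eligibility criteria as a type of deviation to be classified before database lock. That review needs data on what officers were taking at dosing.

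**Working it through.** The plan states no figure for this point, so the check sets the schedule against the reporting window. Visit timings come from Protocol 5.1 and 9.0, the medication marks from Protocol 9.0 and SAP 2.6, and the window from SAP 6.4.

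| Visit | Timing | Medication record scheduled | Inside SAP 6.4 window |
|---|---|---|---|
| 1 | up to 3 months before first training | yes | no |
| 2 | within one week of first training | no | no |
| 3 | shooting day; randomisation and dose | no | yes (opens) |
| 4 | within 24 hours | no | yes |
| 5 | 30 ± 3 days | no | yes (closes) |

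1. *Gap from record to dose.* Up to 3 months, roughly 3 × 30 = 90 days. The limit is tied to the first training session, so the gap could be longer if TTS first appears at a later session.
2. *Length of the SAP window.* From day 0 to Visit 5, at day 30 − 3 = 27 to day 30 + 3 = 33. Where a late visit is accepted under SAP 5.2 (up to 30 days after the scheduled date), it extends to about day 30 + 30 = 60.
3. *Scheduled records after Visit 1.* 0 of 4 visits. Inside the SAP window, 0 of 3.
4. *Could another procedure supply the data?*
   - The Visit 2 items in Protocol 5.1 contain no medication query.
   - Range documentation (5.3) covers session length and rounds, handedness, weapon and hearing protection.
   - The follow-up list (5.4) has no medication item.
   - The Visit 5 questionnaire (Appendix H) asks only about noise.
   - Protocol 10.0 lists forms for consent, eligibility, firearm training and adverse events.
5. *Could the Visit 1 list serve?* Only in part. It can name drugs in use at screening. It has no start or stop dates and is not updated, so it cannot show that a drug was still being taken at dosing, which SAP 6.4 requires of earlier medications. It cannot contain anything started later.

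**The case against.** A fair defence has several parts, and much of it limits how far the point goes.

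- *Eligibility still binds at randomisation.* A reader might infer that the protocol lets ineligible officers be dosed. It does not say so. Protocol 5.2 and SAP 2.4 randomise only eligible participants, and the exclusions in 3.2 are not confined to screening. What is missing is a scheduled query to verify exclusion 8, and a stated time for doing so.
- *The Eligibility Form may be completed twice.* Its schedule can be read as two checks, or as one form finished before training. Either way it precedes shooting, and no medication query is scheduled to inform a second check.
- *Pregnancy is not in the same position.* A reader might extend the 3-month gap to exclusion 5. The serum test is at Visit 2, within a week of training, so a form due before training can carry the result. Officers must also report a pregnancy.
- *The table would not be empty.* The Visit 1 list is a partial source for drugs begun before the dose. Section 10.0 also cannot prove that no medication form exists, because it omits the audiogram and laboratory forms too. The defensible statement is that nothing is scheduled after Visit 1.
- *Some cases would surface.* Adverse events are assessed at Visits 3 to 5, ears are examined at Visits 2, 3 and 5, and deviations are reviewed before lock. Detection is therefore possible, but not systematic.
- *No effect on the treatment comparison is shown.* Randomisation gives no reason to expect drug use before dosing to differ by arm.

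These points narrow the claim. None supplies a medication record near dosing or within the SAP 6.4 window.

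**Conclusion.** The point holds in this form. The protocol text and both calendars schedule one medication record, up to about 90 days before the dose. Exclusion 8 has no stated assessment time and no scheduled medication query between Visit 1 and randomisation. The concomitant-medication table and listing cannot be produced as SAP 6.4 defines them, because 0 of the 3 visits in the window collect the data. The deviation review supporting the per-protocol sample lacks a systematic source for medication-based exclusions.

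The mismatch with SAP 6.4 rests on the text alone. The exclusion 8 part assumes that current use is meant to hold at about the time of dosing. That is a reasonable reading of a criterion about drugs taken alongside study medication, but the protocol does not state it.

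The documents give no rate at which officers start relevant drugs, so the number affected cannot be estimated from them. The primary intention-to-treat test does not depend on these data. The consequence falls on safety reporting, the per-protocol classification and the interpretation of individual Day 30 audiograms. It is worth correcting while data can still be collected prospectively, since medication histories are hard to rebuild reliably afterwards.

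**What to change.** Add the medication record, with start and stop dates, to Protocol 5.4 and to the calendars in Protocol 9.0 and SAP 2.6: at Visit 3 before randomisation, and at Visits 4 and 5. Add start and stop dates to the Visit 1 list so that the later records update it, and show the medication form in Protocol 10.0.

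Reconcile Protocol 3.2, 5.1, 5.4, 9.0 and 10.0 with SAP 2.6 and 6.4 on two matters: when medications are recorded, and at which time point the existing time-varying exclusions are assessed. The choice of time point is for the sponsor and investigator. No exclusion needs new content for this purpose.

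The cost is a calendar and form amendment and a few minutes of questions at visits that already take place. Visit 3 is the tight one: its 5-30 minute slot already holds the ear examination, audiogram, DPOAE (about 20 minutes by Protocol 5.1), randomisation and dose. A few officers may also be found ineligible on the day, which would slightly slow accrual.

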## 5.2 Randomization

Following identification of TTS, eligible participants will be randomized via an interactive randomization tool (IRT) in a balanced fashion into one of two study groups: ZNS (100 mg PO) or placebo. Randomization will be based on a randomization list generated from the study statistician using a computer algorithm written in SAS using randomly selected blocks of sizes 2. Within each block of 2, there will be 1 subject assigned to each study group. To balance noise-exposure history across study arms we will employ stratified randomization. The subjects will be stratified based on noise exposure survey responses (see table below), and will then be randomized to study groups. The random assignment of subjects to the different study groups will be associated with consecutively assigned study identification numbers (Study ID) which will be unique for each study participant. The stratified randomization kit list will be provided to Advanced Rx who will package and label the drug for shipment to the pharmacist for each participant. Each bottle will be labeled with the kit number, study ID, and instructions on how to take the medication. The bottle will not contain any information of the treatment allocation.

- ZNS (100 mg PO) group
- Placebo PO group

Name	Description
1: High Noise	Screening: LENS-Q Adapted for Police Officer

Name	Description
	
1A Or 2A Or 3A =
 
a.Daily, Or b.Less than daily/more than weekly, Or c.Weekly, Or d.Less than weekly/more than monthly Or e.Monthly
 
OR
 
1C Or 2C Or 4C <math>\geq 5</math> Years

2: Low Noise	
Screening: LENS-Q Adapted for Police Officer
 
1A AND 2A AND 3A =
 
f.Less than monthly/more than yearly, g.Yearly, h.Less than yearly Or i.Never
 
OR
 
1C AND 2C AND 4C <math>< 5</math> Years

### **5.3 Testing on the Range (Visit 3)**

1. Duration of each shooting session and number of rounds fired by each participating officer will be documented.
2. Handedness will be documented.
3. Weapon type(s), including caliber and ammunition, used for each participating police officer will be documented.
4. Hearing protection device(s) including type, make, model and noise reduction rating (NRR) used by each participating police officer will be documented.

### **5.4 Follow-Up Assessments (Visits 3, 4 and 5)**

The follow-up assessments will occur after training and include the following tests or procedures:

1. Audiogram and DPOAEs to measure for TTS and auditory changes, as soon as possible after the training session. The exact time of testing following training operations will be documented. A clinical ear exam will be completed prior to the audiogram and DPOAEs. (follow-up visit 3 and 5).
2. Baseline environmental/ambient sound measurements will be recorded at the start of each test session, including the peak ambient noise level and the average noise level (follow-up visit 3 and 5).
3. Collection of blood for laboratory testing to include an electrolyte panel, BUN, Cr, ALT, and AST. This will occur within 12-24 hours following drug intake (follow-up visit 4).
4. Cognitive assessments within 24 hours following drug intake, including (follow-up visit 4):
  - a. Digit-symbol substitution test (processing speed)
  - b. Verbal fluency (working memory, speech/language)
  - c. Stroop (Executive function, inhibition)
  - d. List Learning task/RBANS (memory)

Additionally, after each officer is asked about potential study-related side effects for safety monitoring, they will be asked a question regarding their feeling of safety on the job, i.e. they will be asked *“if they feel safe partaking in required responsibilities associated with their job at this time or not?”*

5. Completion of LENS-Q 1-minute noise screening for noise exposure questionnaire (follow-up visit 5).
6. Audiogram, ECochG, DPOAE, and WIN testing 30 days (+/- 3 days) after each training session to assess for PTS and auditory changes, only if TTS is observed from #1 (visit 5).
7. Documentation of adverse events at all follow-up visits (5-30 minutes post, within 24 hours and at 30 day visit) (follow-up visit 3, 4 and 5).

Follow-up assessments will be planned at the stated time points; actual follow up times may vary due to patient logistics and compliance.

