### **1.2 NIHL and its Pathogenesis**

After noise exposure, two phases of hearing loss can be measured. The first is a temporary threshold shift (TTS), which is greatest immediately after noise exposure, and gradually lessens within the first 24 hours. The second phase is a permanent threshold shift (PTS), which is measured two to three weeks after noise exposure (for recent review, Ryan et al., 2016; Liberman, 2016). These changes are typically monitored using behavioral pure-tone thresholds, distortion product otoacoustic emissions (DPOAE), or the auditory brainstem response (ABR) to generate an audiogram (a plot of threshold as a function of test frequency). The noise-induced damage is dependent on the noise pattern, intensity, and duration, with longer and louder noises being more hazardous than shorter or quieter sound exposures (Wang et al., 2002; Harding and Bohne, 2007; Chen et al., 2015). In addition, NIHL susceptibility differs markedly among individuals, resulting from the interaction of genetic and environmental factors (Clifford et al., 2016; Groth et al., 2016; Lavinsky et al., 2016). For example, in animals, the C57BL/6J mouse strain is more susceptible to noise than other mouse strains (Davis et al., 2001). In humans, individuals with specific single nucleotide polymorphisms (SNPs) in genes for certain antioxidant enzymes may be more susceptible to NIHL (Lin et al., 2009) and a recent study developed a genetic risk score for the likelihood of NIHL based on genetic markers (Zhang et al., 2019). Over 100 loci associated with syndromic and non-syndromic hearing loss provide excellent biomarkers for PGx studies and are easily surveyed in genetic screening protocols (e.g. Pawelczyk et al., 2009; Konings et al., 2009; Grondin et al., 2015). Furthermore, known genetic variation is associated with the metabolism of anti-epileptic drugs including zonisamide (Saruwatari et al., 2010) and could be used to predict patient populations that are both responsive and non-responsive to drug treatments.

Finally, methodologies are currently under development to predict genotypic variation based on audiographic profiles that could in practice be integrated with genetic data (<https://audiogene.eng.uiowa.edu/>) facilitating the statistical analysis of drug efficacy in clinical trials.

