#### **7.1.6 Administration**

Participants will receive one time dose of oral ZNS or matching placebo. Participants will be instructed to take study drug without food. We will recommend that capsules be swallowed whole per the current approved labeling.

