## APPENDIX G: Questionnaire 4: LENS-Q Adapted Survey for Stratification (High vs. Low Noise Exposure Group Stratification)

**LENS-Q Adapted for Police Officer Study:** By virtue of working in a career with required firearm use, all participants are automatically categorized as high noise. The point of this modified survey is to stratify participants into relatively higher and relatively lower exposure groups.

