#### DURING THE PAST 30 DAYS,

1. How often were you around or did you shoot firearms such as rifles, pistols, shotguns, etc.?  
 Never    Less than weekly    Weekly    More than weekly    Daily
2. How often were you exposed to loud sounds while working on a paid job? By loud sounds, we mean sounds so loud that you had to shout or speak in a raised voice to be heard at arm's length.  
 Never    Less than weekly    Weekly    More than weekly    Daily
3. How often were you exposed to any other types of loud sounds, such as power tools, lawn equipment, or loud music? By loud sounds, we mean sounds so loud that you had to shout or speak in a raised voice to be heard at arm's length.  
 Never    Less than weekly    Weekly    More than weekly    Daily

Noise exposure score: \_\_\_\_\_

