2.3 Study Population

This study is a randomized, controlled clinical trial with two parallel groups. Police officers identified with TTS following shooting range noise exposure will be randomized to receive either ZNS (100 mg PO) or a placebo. We plan to enroll approximately 132 subjects (police officers) with TTS over 4 years. Subjects will be randomized in a balanced fashion into one of the two arms: ZNS (100 mg PO) or Placebo.

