2.7 Sample Size Determination for The Primary Efficacy Outcome Measure

Calculation of sample size for this study is based on a balanced design and a one-sided significance level of 0.025. We estimate that among officers identified as being at high risk for permanent hearing loss due to having TTS, the proportion of PTS positive officers 30 days (+/- 3 days) after shooting will be 50%. This is the proportion of PTS positive officers we expect to observe in the placebo group. Thus, for the primary outcome, we estimated that 66 officers per group will provide us with 80.5% power to detect a 50% reduction in the proportion of PTS positive officers (from 50% to 25%) at the 1-sided alpha level of 0.025. A planned total of 132 subjects is to be enrolled and randomized.

We will make all the needed efforts to eliminate drop outs, and due to short term-follow-up of the study subjects in a period we do not expect any drop-outs or lost to follow-up.

All sample size calculations were carried out using PROC POWER procedure in SAS 9.4.

3 Study Outcomes

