12.2 Index of Proposed Listings

Listing Number	Listing Title	Sample Set
Listing 14.3.3.1	Overall Summary of Physical Examination of Ears Results at Screening	Safety Sample Set
Listing 16.1.1	Subject Enrollment and Disposition	All Subjects
Listing 16.1.2.1	Subject Inclusion and Exclusion Criteria	All Subjects
Listing 16.1.2.2	Protocol Deviations	All Subjects
Listing 16.1.3	Demographic Characteristics	All Subjects
Listing 16.1.4	Medical and Surgical History	Safety Sample Set
Listing 16.1.5	Hearing History and Occupation Exposure	Safety Sample Set
Listing 16.1.6	Concomitant Medications	Safety Sample Set
Listing 16.1.7	Study Drug Administration	Safety Sample Set
Listing 16.2.1	Audiogram Results on Hearing Thresholds	ITT Sample Set
Listing 16.2.2	Distortion Product Otoacoustic Emissions (DPOAE) Results	ITT Sample Set
Listing 16.2.3	Electrocochleography (ECochG) Results	ITT Sample Set
Listing 16.2.4	Word in Noise (WIN) Test Results	ITT Sample Set
Listing 16.2.5	LENS-Q Non-Military Occupational Noise Exposure Results	ITT Sample Set
Listing 16.2.6	LENS-Q Military Occupational Noise Exposure Results	ITT Sample Set
Listing 16.2.7	LENS-Q Non-Military Occupational Chemicals Exposure Results	ITT Sample Set
Listing 16.2.8	LENS-Q Military Occupational Chemicals Exposure Results	ITT Sample Set
Listing 16.2.9	LENS-Q Non-Occupational/Recreation Noise Exposure Results	ITT Sample Set

Listing Number	Listing Title	Sample Set
Listing 16.2.10	LENS-Q NON-Occupational/Recreation Chemicals Exposure Results	ITT Sample Set
Listing 16.2.11	Noise Exposure Questionnaire (NEQ) Responses	ITT Sample Set
Listing 16.2.12	Tinnitus Functional Index (TFI) Questionnaire Responses	ITT Sample Set
Listing 16.2.13	Audiologic and Medical History Questionnaire Responses	ITT Sample Set
Listing 16.2.14	Hearing Handicap Inventory for Adults (HHIA-A) Questionnaire Responses	ITT Sample Set
Listing 16.3.1.1	Serious Adverse Events	Safety Sample Set
Listing 16.3.1.2	Adverse Events Resulting in Death	Safety Sample Set
Listing 16.3.1.3	Treatment-emergent Adverse Events	Safety Sample Set
Listing 16.3.1.4	Treatment-emergent Adverse Events leading to Study Drug Interruption	Safety Sample Set
Listing 16.3.1.5	Treatment-emergent Adverse Events leading to Study Drug Withdrawn	Safety Sample Set
Listing 16.3.2.1	Clinical Laboratory Results at Screening: Biochemistry	Safety Sample Set
Listing 16.3.2.2	Pregnancy Test at Screening	Safety Sample Set

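### Visit 5 is timed from the index session and not from the last noise, so a new temporary shift may be counted as PTS

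*Protocol*

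**What the plan says.** **Endpoint.** SAP 3.2 and 7.1.1 code an officer PTS-positive when the Visit 5 threshold minus the baseline threshold is at least 10 dB at any frequency from 2 to 6 kHz; 3.2 adds that one ear is enough. No repeat audiogram is asked for. Protocol 3.1b uses the same 10 dB at 2, 3, 4 and/or 6 kHz to define the TTS that leads to randomisation.

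**What separates the two.** Protocol 1.2 separates them by time since noise. It describes TTS as a shift "which is greatest immediately after noise exposure, and gradually lessens within the first 24 hours", and PTS as what is measured two to three weeks after exposure.

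**Timing of Visit 5.** Protocol 5.4 has "Audiogram, ECochG, DPOAE, and WIN testing 30 days (+/- 3 days) after each training session to assess for PTS and auditory changes", and the Visit 5 footnote in both study calendars also refers to each session. Protocol 7.1.6 states "Participants will receive one time dose of oral ZNS or matching placebo". SAP 3.1 sets the estimand at 30±3 days after randomisation. Neither document asks for a quiet period, or for the time of the last noise exposure, before the Visit 2 or Visit 5 audiogram.

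**Noise between visits.** The 1-Minute Noise Screen (Protocol Appendix H) is completed at Visit 5. It covers the past 30 days and asks, for example, "How often were you around or did you shoot firearms such as rifles, pistols, shotguns, etc", with answers from never to daily. The SAP does not name it in the endpoint definition, covariates, per-protocol sample, sensitivity analyses, tables or listings. Listing 16.2.11 is instead "Noise Exposure Questionnaire (NEQ) Responses", an instrument that is not among the questionnaires in the current Protocol 5.1, 5.4 or appendices.

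**The concern.** An audiogram 30 days after the index session separates that session's TTS from PTS. It does so only if no later noise has come close to the test. Participants are serving officers who stay at work, and Protocol Appendix G says of them: "By virtue of working in a career with required firearm use, all participants are automatically categorized as high noise". An officer who fired or was near loud noise shortly before Visit 5 may show a rise of at least 10 dB that would have faded, and the coding rule counts it as permanent. In the other direction, a Visit 2 baseline taken soon after noise may be raised and so hide a later shift.

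The primary objective concerns permanent shift after the exposure that was treated. New temporary shifts from later, untreated noise add events that the single dose was not given to prevent. They shrink the difference between arms and so the power. A null result would then be hard to tell apart from contamination by later noise, because the time of that noise is not recorded.

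**Working it through.** **Inputs from the documents.** SAP 2.7: 66 officers per arm, PTS 50% on placebo and 25% on ZNS, 80.5% power, with the calculation "based on a balanced design and a one-sided significance level of 0.025". SAP 7.1.1: Fisher's exact test. SAP 2.3: equal allocation.

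**1. The plan's own figure.** The Walters arcsine approximation for Fisher's test gives Φ[(arcsin√(0.50 − 1/132) − arcsin√(0.25 + 1/132)) × √132 − 1.96] = 80.5%, as stated. Exact enumeration of the one-sided test gives 81.3%, which is the reference below.

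**2. Model.** Let f be the share of truly PTS-negative officers, equal in both arms, who carry a fresh shift of at least 10 dB at Visit 5. The observed rate is p + (1 − p)f. This is 0.50 + 0.50f on placebo and 0.25 + 0.75f on ZNS, so the difference is 0.25(1 − f).

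**3. Range for f.** The documents do not give f, so it is an assumption. It is the product of the share of officers exposed shortly before Visit 5 and the share of those who still show 10 dB when tested. If 5%, 10% or 20% are exposed and 40% of them still show a shift, f is 2%, 4% or 8%. If 80% of them do, f is 4%, 8% or 16%.

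**4. Exact one-sided Fisher power, 66 per arm, alpha 0.025.**

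| f (assumed) | Placebo | ZNS | Difference (points) | Power |
|---|---|---|---|---|
| 0 | 50.0% | 25.0% | 25.0 | 81.3% |
| 2% | 51.0% | 26.5% | 24.5 | 78.9% |
| 4% | 52.0% | 28.0% | 24.0 | 76.2% |
| 8% | 54.0% | 31.0% | 23.0 | 70.7% |
| 16% | 58.0% | 37.0% | 21.0 | 60.1% |

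**5. A different reading of the planning rate.** Step 4 takes 50% as true PTS. Suppose instead that 50% already includes the fresh shifts and ZNS halves only true PTS. The true placebo rate is then t = (0.50 − f)/(1 − f), and the observed ZNS rate is t/2 + (1 − t/2)f. For f = 5%, t = 47.4%, the observed ZNS rate is 27.5% and power is 71.1%. For f = 10%, t = 44.4%, the observed ZNS rate is 30.0% and power is 59.0%.

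**6. Type I error.** With equal rates in both arms, from 50% to 60%, the exact size is 1.5% to 1.7%, below 2.5%.

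**The case against.** The strongest reply is that the documents do not show how often this would happen. They do not say that any officer will shoot again before Visit 5. The references to each session are ambiguous: the first item of Protocol 5.4 speaks of a single session, one dose is given, and officers without TTS leave the study. The Appendix G sentence concerns exposure history used for stratification, not noise between Visits 3 and 5. All of this stands, and it is why f is shown as a range.

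Four stronger readings are tempting, and the documents do not support them:

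- **That 24 hours is the recovery time.** Protocol 1.2 says that TTS lessens over the first 24 hours. It does not say that TTS is gone by then, so a 24-hour rule cannot be taken from it.
- **That about 80% of recently exposed officers would show a shift.** Protocol 12.3 takes that rate from military cadets, and 12.4 applies it to officers screened within an hour of shooting. It does not carry over to any loud noise up to a day earlier, so the lower rows of the table lean towards the high side.
- **That contaminated results could never be recognised.** Officers who answer never to all three Appendix H items can be identified from data already planned. What is missing is the time of the last exposure for the others, and a pre-specified use of the answers.
- **That the trial could show a false benefit.** Allocation is random and blinded, so the error should be similar in both arms.

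The baseline half of the point is also softer. The calendar has a second pre-training audiogram at Visit 1 for comparison, and a raised baseline lowers both the PTS count and the chance of qualifying with TTS. No size is claimed for it.

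**Conclusion.** The gap holds. The same 10 dB rule serves for TTS and PTS, and the plan controls the time since the index session but not the time since the last noise. The one instrument that covers noise between visits does not ask when it last occurred and has no role in the SAP. Following the plan as written can therefore count a fresh temporary shift as permanent.

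The consequence is dilution and lost power. Type I error is not inflated. The loss is 2.4 points of power at f = 2% (81.3 − 78.9) and 21.2 points at f = 16% (81.3 − 60.1). These figures assume that f is equal in both arms and that 50% and 25% are true PTS rates. Nothing in the documents says where in that range the trial would fall, and the true value may be small. The point rests on a gap that is cheap to close, not on a demonstrated large loss.

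**What to change.** 1. **Record and schedule (Protocol 5.1 and 5.4).** Before the Visit 2 and Visit 5 audiograms, record the date, time and type of the last firearm or loud-noise exposure. Where the existing windows allow, book these audiograms away from range sessions, with a minimum quiet interval that the sponsor justifies, since Protocol 1.2 gives no recovery time. If no such slot exists, as may happen for officers exposed daily, test anyway so that no primary data are lost.
2. **Reconcile the anchor.** The references to each session in Protocol 5.4 and in both calendars must be reconciled with the single dose in Protocol 7.1.6 and with the estimand in SAP 3.1, so that Visit 5 is tied to the session at which TTS was identified.
3. **Pre-specify the use (SAP 7.1.1).** Add a sensitivity analysis of the primary endpoint that uses the 1-Minute Noise Screen and the last-exposure time. For example, leave out or adjust for officers with firearm exposure after the index session or with recent noise before Visit 5. Keep the ITT analysis primary. In SAP 12.2, list the 1-Minute Noise Screen in place of the NEQ.

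**Cost.** One added question, some rebooking, and a smaller sample in the sensitivity analysis. No new visit, test or staff is needed. SAP 5.2 already accepts Visit 5 data up to 30 days late, so moving a visit need not create missing data.
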